Method and Materials: A total of 24 not well controlled diabetic mellitus (DM) type 2 patients (HbA1c =>7%) with Periodontitis will be recruited. All subjects must have generalized moderate to severe chronic periodontitis. All subjects will be recruited from LLU Health. Subjects will be divided into two group based on their medical needs: HBO therapy and Non HBO therapy. For all subjects demographic data (age, gender, ethnicity, smoking history, alcohol use history, BMI, current medication list) and oral health habits will be obtained. Blood samples for HbA1c determinations, clinical periodontal measurements (plaque index, probing measurements including pocket depth, attachment levels, gingival index and bleeding-on-probing) and subgingival microbial samples will be obtained at baseline and end of the study. Subgingival microbial samples will be collected from three randomly selected sites with probing depth =>5mm and pooled together in a single tube. Both groups will receive full-mouth SRP. The HBOT group will also receive oxygen therapy protocol.

Microbiological Analysis: Collected microbial samples will be processed for DNA extraction and stored at -80°, then sent to the Forsyth Institute (Cambridge, MA) for HOMINGS analysis (The Human Oral Microbe Identification Microarray (HOMIM) technology for detection of about 300 of the most prevalent oral bacterial species, including many that cannot be grown in the laboratory using 16S rRNA gene sequencing).

Statistical analysis: Differences in periodontal clinical outcomes and bacterial profiles from baseline to 12 weeks between non-hyperbaric therapy group and hyperbaric therapy group will be analyzed using the repeated measures ANCOVA (Analysis of Covariance) procedure for paired observations. Periodontal clinical measures at baseline and later time-points will comprise the dependent variables. The ANCOVA procedure will help to account for patient differences in demographics and other clinical factors at baseline while also adjusting for effects of confounding factors.

Hypothesis: “The combination therapy of HBOT and SRP in patients with not well controlled DM type2 and periodontal disease will improve the periodontal clinical parameters and reduce subgingival microbial load.”

Time line and Milestones:

We anticipate a period of one year to complete the proposed research.

Protocol Submission and Approval: September 2015

Preparations, team training and calibration: 10/1/15-10/30/15

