Patient recruitment, examination visits, medical evaluation and commencement, lab tests, data entry, treatment, follow-up: 11/01/2015-05/30/2016

Data analysis, manuscript writing, and final report preparation: 06/01/2015-08/30/2016

REASERCH PROPOSAL

PROJECT TITLE:

“Hyperbaric Oxygen as Adjunctive Therapy to Scaling and Root-Planing in the Management of Periodontitis in Poorly Controlled Diabetics Type 2.”

Specific Aims (Statement of Purpose):

Our central hypothesis is based on the fact that hyperbaric oxygen (HBO) therapy expose patients to 100% oxygen at an accompanied high pressure (at 2-3 atmospheres absolute, ATA) to induce a state of hyperoxygenation which has an immediate effect (occurring while the patient is within the HBO chamber) and many other delayed effects (which occurs many days or weeks after the initiation of the course of therapy). Immediate effect involves increased oxidative killing by neutrophils and direct killing of anaerobic organisms and organisms that use oxygen as a substrate, due to high-pressure oxygen saturation in their cytoplasm. The delayed effect (which manifests between 8-10 treatments) involves: the release of growth factors such as PDGF and VEGF, and promoting neovascularization along with hypergranulation that would enhance wound healing. We hypothesize that these effects would improve the gingival tissue healing response following non-surgical periodontal therapy and would also decrease the subgingival microbial load.

We plan to test our central hypothesis and thereby accomplish the objective of this application by pursuing the following specific aims:

1) Evaluate the adjunctive effect of HBO therapy on the clinical outcomes of non-surgical periodontal therapy (scaling/root planing, SRP).

Our working hypothesis, based on previous evidence: SRP as the current standard of care is not fully successful in restoring periodontal tissue health in not well controlled diabetics. HBO therapy as an adjunctive treatment with SRP would bring significant enhancement on tissue healing and improve clinical periodontal outcomes.

2) Examine the adjunctive effect of the HBO therapy on subgingival microbial profile.

Our working hypothesis, based on previous evidence: HBO therapy as an adjunctive treatment with SRP would cause a significant reduction in levels of anaerobic bacteria, furthermore the effect would persist for an extended period (in 3 months).

Background (Review of Literature):

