In summary: DM is a growing chronic health problem in the United States and the world. It is a well-established risk factor for periodontal disease. Periodontitis in turn can increase insulin resistance and potentially aggravates diabetes. Managing periodontitis in diabetics is important. However, poorly controlled diabetics do not respond favorably to periodontal therapy. HBOT as an adjunctive therapy, along with SRP, has promise to improve the outcomes of non-surgical periodontal therapy and reduce subgingival microbial load in poorly controlled diabetics. It may also have greater impact on the subgingival microbial profile than SRP alone. The main objectives of the research are investigating the combined effect of both therapies vs. the effect of SRP alone on the periodontal clinical outcome as well as the subgingival microbial profile in poorly controlled diabetics.

Hypothesis: “The combination therapy of HBOT and SRP in patients with not well controlled DM and periodontal disease will improve the periodontal clinical parameters and subgingival microbial profiles due to HBOT immediate and delayed effects on neovascularization, growth factors, osteogenesis, PMN’s killing function, and oxygen saturation in anaerobic bacterial cytoplasm.”

Alternative hypothesis: Combination therapy of HBOT and SRP in patients with poorly controlled DM and periodontal disease will not have a significant improvement on the periodontal clinical parameters and subgingival microbial profiles.

RESEARCH DESIGN AND METHODS

The Approach:

Study Design: The proposed pilot study is a longitudinal observational study to compare periodontal treatment (SRP) outcome between 2 diabetic patient groups receiving medical care at LLUMC either with or without adjunctive Hyperbaric Oxygen Therapy. The results will provide essential preliminary data to plan for an R21 NIH study that will be powered to comprehensively assess treatment outcomes and better understand the mechanisms involved.

Subject Characteristics:

All subjects will be recruited from the diabetic patient pool at LLU Health. Drs. [name] and [name] at their respective institutions will work together to identify and refer prospective subjects to the study. All subjects must have not well controlled DM type 2 (as defined below). In addition, all subjects must have generalized moderate to severe chronic periodontitis (as defined below).

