For bacterial DNA extraction, 44 mL of each sample will be taken, and 0.5% polysorbate 20 and 1 mL of protease K (10 mg/mL) will be added. The samples will be heated at 55°C for 2 hours and at 95°C for 5 minutes for inactivation of protease K. All samples will be stored in a freezer at -80°C before polymerase chain reaction (PCR) amplification. The HOMIM methodology will be used here was described in detail in a previous study. Briefly, a total of 400 16S rRNA-based, reverse-capture oligonucleotide probes targeting >300 bacterial taxa. 16S rRNA genes are PCR amplified from DNA extracts using 16S rRNA universal forward and reverse primers and labeled via incorporation of cyanine 3-deoxycytidine triphosphate in a second nested PCR. The labeled 16S amplicons will be hybridized overnight to probes on the slides. After washing, the microarray slides will be scanned and crude data will be extracted using software for microarray image analysis. Data will be normalized by comparing individual signal intensities to the average of signals from universal probes (Ahn et al., 2011; Colombo et al., 2012; Lourenco et al., 2014)

Statistical Analysis:

[name], Assistant Professor, Loma Linda University School of Dentistry, Department of Dental Research, will perform statistical analysis.

Power Analysis:

To detect a difference of 2 mm in average pocket depth between the Non HBO+SRP and HBO+SRP treatment groups and assuming a standard deviation of 1mm, the study would need to have 12 subjects in each group to have an 80% chance of detecting the stated effect, at an alpha level of 0.05.

Hypothesis Testing:

We plan to test our central hypothesis and thereby accomplish the objective of this objective of this application by pursuing the following specific aims:

1) Evaluate the effect of HBO therapy on clinical outcomes of SRP.

Our working hypothesis, based on previous studies on SRP as a current standard of care in the non-surgical periodontal therapy, is that SRP alone is not fully successful in restoring tissue health and clinical outcomes such as GI, PPD, CAL, and BOP. The HBO therapy with SRP may have a synergic effect on enhancing blood supply, osteogenesis, and promoting growth factor production and can cause significant enhancement on tissue healing and clinical periodontal outcomes.

Statistical analysis:

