Differences in pocket depth from baseline to 12 weeks between the Conventional Wound Healing group and Hyperbaric Therapy group will be analyzed using the repeated measures ANCOVA (Analysis of Covariance) procedure for paired observations. Periodontal clinical measures at baseline and later time-points will comprise the dependent variables. The ANCOVA procedure will help to account for patient differences in demographics and other clinical factors at baseline while also adjusting for effects of confounding factors.

2) Examine the effect of the HBO therapy on subgingival microbial profile.

Our working hypothesis, based on initial effect stage of HBO therapy, is significant reduction and low levels of anaerobes bacteria persist after 3 months of combination therapy compare with only current standard periodontal treatment.

Statistical analysis:

Differences in bacterial counts from baseline to 12 weeks between the Conventional Wound Healing group and Hyperbaric Therapy group will be analyzed using the repeated measures ANCOVA (Analysis of Covariance) procedure for paired observations. Bacterial counts as measured at baseline and later time-points will comprise the dependent variables. The ANCOVA procedure will help to account patient differences in demographics and other clinical factors at baseline while also adjusting for effects of confounding factors.

Potential difficulties and limitations:

Antibiotic medications:

Antibiotic medications used in conventional wound care may influence the clinical and microbial factors we are measuring. To control for their potential influence, we will keep a log of all medications and doses. Subjects enrolled in the proposed study will not be asked to refrain from their antibiotics and other medications as part of their wound healing treatment prior to examination and sampling. We will collect our baseline data after the subjects start their medication regimen. Thus, the subgingival bacterial samples and clinical parameters recorded at baseline will account for antibiotic use prior to periodontal intervention. Furthermore, in our statistical analysis we will adjust for the number and class of medications.

Study Design: We elected to go for a longitudinal observational design because of budget limitation. Our objective is to collect pilot data to enable us to seek external funding for a fully powered “Randomized Clinical Trial”.

References:

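### The plan predicts a lower subgingival microbial load and analyses bacterial counts, but describes no measure of total bacteria

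*Combined protocol and SAP*

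**What the plan says.** The plan words its microbial outcome in two ways.

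- **As an amount.** The Abstract hypothesis says the combination "will improve the periodontal clinical parameters and reduce subgingival microbial load". The Specific Aims say the HBOT effects "would also decrease the subgingival microbial load". The summary paragraph that closes the Background also speaks of reducing load. The Aim 2 working hypothesis in the Specific Aims says adjunctive HBOT "would cause a significant reduction in levels of anaerobic bacteria", and Hypothesis Testing repeats the idea as low anaerobe levels that persist at 3 months. The Aim 2 statistical analysis then states: "Bacterial counts as measured at baseline and later time-points will comprise the dependent variables".
- **As a profile.** The Abstract's statistical analysis concerns "Differences in periodontal clinical outcomes and bacterial profiles from baseline to 12 weeks". The formal hypothesis after the Background says the combination "will improve the periodontal clinical parameters and subgingival microbial profiles due to HBOT immediate and delayed effects". The Aim 2 heading under Hypothesis Testing reads "Examine the effect of the HBO therapy on subgingival microbial profile".

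Microbiological Sampling takes plaque by curette from three sites and pools it. The examiner and sites are the same at each visit and the buffer volume is stated, but no amount of plaque is fixed or measured. Microbiological Analysis describes DNA extraction from a stated aliquot, PCR with universal 16S primers, a second nested PCR for labelling, and hybridisation to the HOMIM array. It ends: "Data will be normalized by comparing individual signal intensities to the average of signals from universal probes".

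The Abstract and the opening of Microbiological Analysis name HOMINGS, and the Abstract also mentions 16S sequencing.

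**The concern.** A statement about load or counts needs a quantity that falls when there are fewer bacteria. A signal divided by a reference from the same sample need not do so, because numerator and denominator can fall together. If such signals were analysed under the name of counts, a real effect on total load could be missed. An apparent rise in taxa that HBOT does not affect could also be taken at face value.

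The study is a pilot, but its results are meant to support the next grant application. An unsupported statement on load would carry forward into that application.

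**Working it through.** The plan gives no sample size, effect size or variance for Aim 2 (the power statement concerns pocket depth), so there is no figure to reproduce. The check has two parts.

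**1. Is total bacteria measured anywhere?** The microbiology and analysis sections describe no quantitative PCR, culture count, DNA yield, plaque weight, spike-in or calibration standard. The universal-probe signal appears only as the normaliser, after two PCR rounds, and is not planned as an outcome. The plaque index and the supragingival plaque record are clinical scores and do not measure subgingival bacteria. Nothing further is described for HOMINGS or sequencing. The gap therefore exists on either platform.

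**2. What would a within-sample ratio do?** This part is an illustration. It assumes that the normalisation divides each signal by a total from the same sample and that signal is proportional to abundance. Both groups receive SRP, so the effect is the extra change with HBOT beyond SRP alone.

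- f = true ratio for anaerobes, HBOT plus SRP against SRP alone. Assumed 0.10 (tenfold fall) or 0.50 (twofold fall).
- p = anaerobe share of signal at 12 weeks after SRP alone. Assumed 50%, 70% or 90%; the documents give none.

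*Equal fall in all taxa.* A taxon with signal s and universal signal U reads (f × s)/(f × U) = s/U. There is no change for any f.

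*Selective fall in anaerobes.* The new total is T = f × p + (1 − p). Anaerobes read f/T, unaffected taxa read 1/T, and the share of the true log change that remains is ln(f/T)/ln(f).

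| f | p | T | Anaerobes read | Unaffected taxa read | Log change kept |
|---|---|---|---|---|---|
| 0.10 | 0.5 | 0.55 | 0.18 | 1.8 | 74% |
| 0.10 | 0.7 | 0.37 | 0.27 | 2.7 | 57% |
| 0.10 | 0.9 | 0.19 | 0.53 | 5.3 | 28% |
| 0.50 | 0.5 | 0.75 | 0.67 | 1.3 | 58% |
| 0.50 | 0.7 | 0.65 | 0.77 | 1.5 | 38% |
| 0.50 | 0.9 | 0.55 | 0.91 | 1.8 | 14% |

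Worked example for f = 0.50, p = 0.5: ln(0.5/0.75)/ln(0.5) = 0.585, or 58%.

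*Ratio of anaerobes to the rest.* (f/T)/(1/T) = f, so T cancels and the ratio returns 0.10 or 0.50 in the matching rows. The limit of this ratio shows in one case. Start with anaerobes 50 and the rest 50. If the rest doubles, the ratio is 50/100 = 0.5. If anaerobes halve instead, it is 25/50 = 0.5. The ratio cannot tell these apart, although the total rises to 150 in one case and falls to 75 in the other.

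**The case against.** The strongest reply is that this is mainly a matter of wording. The study is a pilot sized on pocket depth. The Aim 2 heading, the formal hypothesis and the Abstract's analysis already say profile. Counts could mean sequence reads or numbers of taxa detected, neither of which is a statement about load. Sampling is partly standardised, and the array method is given only in brief, with reference to earlier publications.

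Much of this stands. It lowers the weight of the point and leaves the exact normalisation open. It does not remove the mismatch. Load is predicted in three places, and the only detailed Aim 2 analysis names counts without defining them. Same examiner, sites, buffer volume and aliquot do not fix the amount of plaque collected.

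A reader might go further and infer that Aim 2 cannot be answered, or that the assay is known to return purely relative values. The documents support neither. A shift in composition can still be studied, and the ratio reading of the normalisation is an inference. Nor do they show that load will be misreported, since the meaning of counts is unsettled.

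The figures in the table have no input from the documents. They also depend on proportional signal, and two PCR rounds with no stated calibration may not deliver that.

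**Conclusion.** The point holds in this form: no measure of total bacteria is described on either named platform, so the data as described do not support a conclusion on microbial load or absolute counts. This rests on the text alone.

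The distortion is conditional on a within-sample ratio and proportional signal. Under those assumptions an equal extra fall is invisible. A selective fall in anaerobes is seen in the right direction but understated, keeping between 14% and 74% of its log change over the assumed range, while unaffected taxa appear to rise 1.3- to 5.3-fold. These figures show the kind of error possible and do not estimate its size in this study.

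The plan should be changed, but the point does not threaten the pocket-depth aim. Confidence is medium because the normalisation is not fully specified.

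**What to change.** 1. Reconcile the platform first: HOMINGS or sequencing (Abstract; opening of Microbiological Analysis) against the HOMIM array (technique described later in that section).
2. Replace load with relative composition (microbial profile) in the Abstract hypothesis, the Specific Aims and the Background summary. Do the same for bacterial counts in the Aim 2 statistical analysis.
3. Restate the Aim 2 working hypotheses on anaerobe levels, in the Specific Aims and under Hypothesis Testing, as relative to the other taxa measured.
4. State that no conclusion on load or absolute counts will be drawn.
5. Make the Aim 2 outcome the log ratio of summed signal for a pre-listed set of anaerobic taxa to that of the remaining taxa at 12 weeks, with the baseline log ratio as covariate.

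A common multiplicative factor per sample cancels in this ratio. Additive background, saturation and undetected taxa do not, so their handling should be stated.

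The cost is wording, a taxon list and one defined variable, with no new assay. The downside is that no claim on total load can be made, and the ratio cannot separate a fall in anaerobes from a rise in other taxa. Keeping the load claim would instead need a separate total-bacteria assay on each sample and a measured amount of plaque. Averaging probes within a taxon and false discovery rate control for single-taxon tests are optional and not part of this correction.

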A total of 24 not well controlled type 2 diabetic subjects with Periodontitis presenting for medical care at LLU Health will be recruited for the study (see power analysis under statistical section). An additional 6 subjects will also be recruited to compensate for subject attrition. Subjects will be divided into two group based on their medical needs: HBO therapy and Non HBO therapy. For all subjects demographic data (age, gender, ethnicity, smoking history, alcohol use history, BMI, current medication list) and oral health habits will be obtained. HBOT subjects will be recruited first and control subjects (non HBO group) will be recruited after to match the HBO subjects on all parameters including HbA1c level to minimize bias.

Inclusion Criteria:

Diabetic patients must meet the following inclusion criteria:

1. An established diagnosis of DM type 2 (HbA1c =>7%).
2. Subjects must have a minimum of 10 permanent teeth.
3. Age range 35 year or older.
4. All subjects must be registered patients at LLU Health.

Exclusion Criteria:

Individuals with the following conditions may NOT participate in the study:

1. Well-controlled type 2 diabetics (HbA1c <7%) and type 1 diabetic patients.
2. Other systemic conditions with known association with periodontitis, e.g. AIDS, Down's syndrome, current smoker, head and neck radiation, Xerostomia, currently under chemotherapy.
3. Intra-oral conditions present which might interfere with accuracy of periodontal probing, e.g. gingival overgrowth, orthodontic wires, excessive calculus.
4. Not a registered patient at LLU Health.
5. Overweight/obese individuals (BMI greater than 45 %)
6. Pregnancy or lactation

[figure not shown]
QUESTIONNAIRE:

Oral Health Interview: subjects will be interviewed regarding personal and professional dental care habits and cigarette smoking habits.

Study Plan:

Group	Not eligible for HBOT N=15	Eligible for HBOT N=15
Medical History Review Medical Assessments	Yes	Yes
Baseline HbA1c	Yes	Yes
Baseline Periodontal Evaluations	Yes	Yes
SRP	Yes	Yes
HBO Therapy	No	Yes (20-40 daily treatments for 8 weeks)
Final Periodontal Evaluation (12 weeks after SRP)	Yes	Yes
Final HbA1c (12 weeks after SRP)	Yes	Yes

Note: subjects in both groups will be receiving any needed medical care

CLINICAL EVALUATIONS

Medical Assessments:

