Determination of diabetes status: review of medical history and Hemoglobin A1C testing will be done under the direction of [name] or qualified residents. All subjects entered in the study will go through a comprehensive medical evaluations and blood testing to determine the diabetic status.

Dental/Periodontal Examination:

[name] will direct and supervise all dental/periodontal examinations. The dental examiners will be blinded to HBOT therapy status. At initial examination and 4 weeks after HBOT, all subjects will undergo comprehensive oral evaluations followed by recoding of the Loe 1967 gingival index (GI), periodontal probing measurements (PPD), bleeding on probing (BOP), clinical attachment loss (CAL), and Quigley & Hein plaque index (PI). Average scores will be computed for each measure per subject.

Periodontal Probing Measurements:

All fully erupted teeth present, excluding third molars, will be measured. A pressure controlled periodontal probe (Williams Probe, with 1mm marking, Hu-Friedy) will be used to determine probing depth at six sites per tooth: mesiobuccal, buccal, distobuccal, mesiolingual, lingual, distolingual. The position of the gingival margin in relation to the cementoenamel junction will also be recorded at the same 6 sites per tooth to the nearest mm. A negative sign will be given

when the gingival margin is coronal to the cementoenamel junction and a positive sign will be given when it is apical. Clinical attachment level (CAL) will be calculated by adding probing depth to position of gingival margin. Percentage of teeth with at least one site having loss of attachment (CAL) ≥ 5 mm will be calculated for each subject. Also, the presence or absence of gingival redness, suppuration, bleeding on probing (BOP), and supragingival plaque accumulation will be recorded. Clinical measurements will be taken at baseline and at 3 months post-therapy.

Periodontitis diagnosis:

Periodontal diagnosis will be based on the 1999 AAP Classification of Periodontal Diseases. Diabetic individuals with Chronic Periodontitis will be recruited for the study. Selected subjects must have 5% or higher of scored teeth with attachment loss ≥ 5 mm and probing depth ≥ 5 mm.

Treatment Protocol:

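### The stated 12 per group for 80% power does not follow from 2 mm, SD 1 mm and alpha 0.05: an unadjusted two-sided t-test needs 6 per group, and 12 give about 99.7%

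*Combined protocol and SAP*

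**What the plan says.** The Power Analysis paragraph under Statistical Analysis sets the target: "To detect a difference of 2 mm in average pocket depth between the Non HBO+SRP and HBO+SRP treatment groups". It continues: "assuming a standard deviation of 1mm, the study would need to have 12 subjects in each group to have an 80% chance of detecting" the effect, at an alpha level of 0.05. It names no test, sidedness or covariates. It does not say whether the SD is for the 12-week value or for change, and it gives no source for the 2 mm or the 1 mm.

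Other sections bear on the number:

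- **Subject Characteristics** rests the total of 24 on this paragraph: the subjects "will be recruited for the study (see power analysis under statistical section"). It then adds: "An additional 6 subjects will also be recruited to compensate for subject attrition". The Study Plan table accordingly shows 15 per group. Allocation is not random: "Subjects will be divided into two group based on their medical needs".
- **Dental/Periodontal Examination** fixes the unit of analysis: "Average scores will be computed for each measure per subject".
- **Hypothesis Testing, aim 1**, describes the outcome as "Differences in pocket depth from baseline to 12 weeks between the Conventional Wound Healing group and Hyperbaric Therapy group", analysed by repeated measures ANCOVA. It adds: "The ANCOVA procedure will help to account for patient differences in demographics and other clinical factors at baseline".
- **Potential difficulties and limitations** adds adjustment for the number and class of medications. No section says how many covariate terms the model will hold.

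**The concern.** A difference of two standard deviations is very large, and a comparison of two means needs few subjects to detect it. Twelve per group is about twice what such a calculation gives. So at least one of the difference, SD, power, sample size or method is either misstated or left out, and the text does not show which.

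This paragraph is the only basis given for the sample size. If the 2 mm and 1 mm are right, the study has ample power for its target. If the calculation really used a smaller difference, a larger SD or an adjusted model, the margin may be small or absent. The Study Design section says the results will be used to plan a later powered study, so readers should be able to trace the planning inputs.

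**Working it through.** **Inputs from the Power Analysis paragraph:** difference 2 mm, SD 1 mm, alpha 0.05, 80% power, 12 per group. Two-sided testing is an assumption, because the document does not say.

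**Formula.** For a two-sample t-test with n per group, d = difference/SD, df = 2n − 2, and noncentrality λ = d·√(n/2). Power is the probability that a noncentral t(df, λ) exceeds the two-sided 5% critical value.

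**1. The plan's figure on its own inputs** (d = 2/1 = 2)

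| n per group | df | critical t | λ | power |
|---|---|---|---|---|
| 5 | 8 | 2.306 | 3.162 | 79.1% |
| 6 | 10 | 2.228 | 3.464 | 87.6% |
| 12 | 22 | 2.074 | 4.899 | 99.7% |

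The smallest n with at least 80% power is 6. A one-sided test needs 4 (80.2%), which is further from 12. Working backwards, 12 per group and 80% power imply d ≈ 1.20, that is, a difference of about 1.2 mm with SD 1 mm, or an SD of about 1.67 mm with a difference of 2 mm.

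**2. SD read as a single-visit SD.** Aim 1 analyses change. If 1 mm applies at each visit and the visits are uncorrelated (assumption; a positive correlation would reduce the SD), the change SD is √(1² + 1²) = 1.41 mm and d = 2/1.41 = 1.41. Power is 74.9% with 8 per group, 80.4% with 9 and 91.1% with 12. This still does not give 12.

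**3. Attrition.** The allowance is added afterwards (24 + 6 = 30), so it is not contained in the 12.

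**4. Several sites per mouth.** Each subject contributes one average, so no clustering inflation applies.

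**5. Multiplicity.** None is stated. A Bonferroni split over 20 tests would need 10 per group; 12 is reached only at around 50 tests.

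**6. Covariate adjustment.** Assume k covariates with no prognostic value and only chance imbalance between groups. Error df falls to 2n − 2 − k. The information on the group effect is multiplied by a tolerance distributed as Beta((2n − 1 − k)/2, k/2). At n = 12 the mean variance inflation is 21/(21 − k): 1.24 for k = 4, 1.40 for k = 6 and 2.33 for k = 12. Power at 12 per group:

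| k | SD 1 mm | change SD 1.41 mm |
|---|---|---|
| 0 | 99.7% | 91.1% |
| 4 | 98.4% | 83.9% |
| 6 | 96.8% | 78.9% |
| 8 | 94.2% | 72.8% |
| 12 | 83.0% | 56.8% |

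Under this model, 12 is the smallest adequate group size when k is 11 or 12 (SD 1 mm) or 4 or 5 (change SD 1.41 mm). For example, with k = 4 and change SD 1.41 mm, power is 79.3% with 11 per group and 83.9% with 12. Prognostic covariates would raise these powers; systematic imbalance between the groups would lower them.

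**7. Detectable difference at 80% power, 12 per group**

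| SD | k = 0 | k = 12 |
|---|---|---|
| 1 mm | 1.20 mm | 1.91 mm |
| 1.41 mm | 1.69 mm | 2.70 mm |

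**The case against.** The strongest reply is that the benchmark is a test the protocol does not plan. The planned analysis is an adjusted repeated measures ANCOVA, and step 6 shows that 12 per group can be the right answer for an adjusted model. On that view the statement is incomplete rather than wrong. It is also a pilot, the discrepancy errs on the safe side, and no subject, endpoint or conclusion changes.

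Much of this stands. The discrepancy is conservative on the stated inputs, and an adjusted calculation may lie behind the 12. But the power sentence mentions no adjustment, and the scenarios that reach 12 need inputs found nowhere in the document: either 11 or 12 non-prognostic covariates in 24 subjects, or 4 or 5 together with zero correlation between visits. An explanation the reader has to supply confirms that an input is missing.

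It is also fair to say that the covariate grid is illustrative. Subject Characteristics plans to match controls to the HBO subjects, which the chance-imbalance model ignores, and the 2.70 mm figure combines two extremes. The grid shows how much depends on the unstated inputs; it does not predict the study's power.

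Finally, a bare 99.7% in the protocol could mislead, because the groups are formed by medical need and the analysis will be adjusted. That is a reason to label the figure as unadjusted, not to leave the 80% in place.

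**Conclusion.** The concern holds. For the stated 2 mm, SD 1 mm and alpha 0.05, an unadjusted two-sided two-sample t-test needs 6 per group, not 12, and 12 per group give about 99.7% power, not 80%. Reading the SD as a single-visit value narrows the gap (9 per group; 91.1% at 12) but does not close it. The claim is limited to an unadjusted test. An adjusted calculation could give 12, but none is described. The study is not shown to be too small for 2 mm. The defect is that its only sample-size justification cannot be reproduced, while the difference detectable at 80% power ranges from 1.20 to 2.70 mm over the SD readings and covariate counts examined. This should be fixed.

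**What to change.** In the Power Analysis paragraph:

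1. Confirm the 2 mm and the 1 mm and give the source of each.
2. Say whether the SD is for the 12-week value or for change from baseline.
3. Name the test, the sidedness and the number of adjustment covariates, then restate the power.

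If the SD of 1 mm stands, the text could read:

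> With 12 evaluable subjects per group, an SD of 1 mm for the analysed quantity and an unadjusted two-sided two-sample t-test at 0.05, power is about 99.7% for a 2 mm difference and 80% for a difference of about 1.2 mm. Covariate adjustment in the planned ANCOVA may change these figures.

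The 1.2 mm is what the fixed sample size can detect, not a new target. If the 12 came from an adjusted calculation, report its covariates and SD instead.

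The cost is wording only. The 24 subjects and the 6 added for attrition stay as they are.
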